13.1 Waiver of Documentation

Check if VA related

Screening Consent

Title : Woebot for Substance Use Disorders Phase 2 RCT: Digitally Delivered Intervention for Reducing Problematic Substance Use (SU sIRB) Short name: Anchor Study

Approval Period: 03/17/2023 - 05/11/2023

a) Describe the informed consent process. Include the following.

- i) Who is obtaining consent? (The person obtaining consent must be knowledgeable about the study.)
- ii) When and where will consent be obtained?
- iii) How much time will be devoted to consent discussion?
- iv) Will these periods provide sufficient opportunity for the participant to consider whether or not to participate and sign the written consent?
- v) What steps are you taking to minimize the possibility of coercion and undue influence?
- vi) If consent relates to children and if you have a reason for only one parent signing, provide that rationale for IRB consideration.

(i) IRB Modification 3/10/23: Study staff will be obtaining the screening consent via online platform (Qualtrics). The screening questionnaire consent page requests that the potential participant save a copy of the screening consent form. Study contact information is on the consent should any questions come up. (ii) IRB Modification 3/10/2023: This consent will be at the beginning of the screening questionnaire (via Qualtrics). Since consent is obtained online, it can be obtained at any location of potential participants' choosing. If the potential participant is not a US resident, they will be screened out on this question in the screening. Potential participants would be able to rescreen as long as they sign their screening consent each time. (iii) IRB Modification 3/10/23: There is no time limit- each respondent can take much time as they want to read through the consent. Reading the screening consent is anticipated to not take more than five minutes. Contact information is available on the consent form if any questions come up. The screening consent forms can be obtained via download on the Qualtrics . Qualtrics can store data securely. (iv) Since consent is obtained online, the participant may take as much time as they wish to consider whether or not to participate and proceed with the screener. Study staff will not be with the potential participant and there will be no possibility of coercion or undue influence. (v) No incentive or form of coercion is present for the screening process. The study is voluntary; Potential participants are informed that they can withdraw or choose not to participate at any time. There is no payment for going through the screener. (vi) N/A. If under 18 years of age, the respondent will be screened out on the age question.

b) What is the Procedure to assess understanding of the information contained in the consent? How will the information be provided to participants if they do not understand English or if they have a hearing impairment? See HRPP Chapter12.2 for guidance.

We are not recruiting participants who cannot understand English.

c) What steps are you taking to determine that potential participants are competent to participate in the decision-making process? If your study may enroll adults who are unable to consent, describe (i) how you will assess the capacity to consent, (ii) what provisions will be taken if the participant regains the capacity to consent, (iii) who will be used as a legally authorized representative, and (iv) what provisions will be made for the assent of the participant.

Participants will be reading the consent form before beginning the screener. Participants must be English literate to participate as the questionnaires, consent forms, communications, and Woebot app are only available in English. The participant will have to sign the screening consent form to participate in the study. Contact information is also provided during consent for the participant to use if they have questions about the study.

Select ALL applicable regulatory criteria for a Waiver of Documentation and provide a protocol-specific justification:

- 1) **45 CFR 46.117(c)(1)(i), that the only record linking the participants and the research would be the consent document, and the principal risk would be potential harm resulting from a breach of confidentiality; each participant (or legally authorized representative) will be asked whether he/she wants documentation linking the participant with the research, and the participant's wishes govern.**
- 2) **Y 45 CFR 46.117(c)(1)(ii), that the research presents no more than minimal risk of harm to participants and involves no procedures for which written consent is normally required outside of the research context.**
- 3) **45 CFR 46.117(c)(1)(iii), if participants or legally authorized representatives (LAR) are members of a distinct cultural group in which signing forms is not the norm, the research presents no more than minimal risk and there is an appropriate alternative mechanism for documenting that informed consent was obtained.**
- 4) **Y 21 CFR 56.109(c)(1), presents no more than minimal risk of harm to participants and involves no procedures for which written consent is normally required outside of the research context.**

Rationale for above selection:

This consent is for eligibility to participate in the study. The screening questionnaire has been

Title : Woebot for Substance Use Disorders Phase 2 RCT: Digitally Delivered Intervention for Reducing Problematic Substance Use (SU sIRB) Short name: Anchor Study

Approval Period: 03/17/2023 - 05/11/2023

updated to meet waiver of documentation criteria. To meet the criteria for a waiver of documentation (i.e., minimal risk of harm), we have grouped assessment of sensitive (e.g., opioid use) with nonsensitive items (e.g., pregnancy) with a single yes/no assessment to determine eligibility and to avoid having sensitive information on participants. The screening questionnaire includes a few select items from valid and reliable scales, not the full measures except for the CAGE-AID. To help with obtaining a diverse sample, the screening questionnaire includes questions on race/ethnicity, with an option to select Prefer not to Answer if respondents are not comfortable with providing a response. Contact information will be asked if screened eligible.

13.2 Alteration of Consent

Phase 2 ICF - Alteration of Consent

Check if VA related

a) Describe the informed consent process. Include the following.

- i) Who is obtaining consent? (The person obtaining consent must be knowledgeable about the study.)
- ii) When and where will consent be obtained?
- iii) How much time will be devoted to consent discussion?
- iv) Will these periods provide sufficient opportunity for the participant to consider whether or not to participate and sign the written consent?
- v) What steps are you taking to minimize the possibility of coercion and undue influence?
- vi) If consent relates to children and if you have a reason for only one parent signing, provide that rationale for IRB consideration.

(i) Consent will be obtained via REDCap Cloud. Once the informed consent form is fully signed, the potential participant will be notified by email that their consent form is fully signed, and they can go onto REDCap Cloud to download a copy of the fully signed consent form. Each potential participant going through consent will receive an invite from REDCap Cloud via email to create a REDCap account, make a password, and then would be able to read and sign consent. The person obtaining consent will receive an email ping that the consent form is ready to be reviewed and signed. The person obtaining consent can access the form on REDCap Cloud, then review and sign the form. (ii) The online consent can be obtained at anytime and place the potential participant would like. If the respondent is not a US resident, they will be screened out on this question in the screening. For reconsenting, the study team will reach out to the participant about this, and a new consent form invitation from REDCap Cloud will be sent. (iii) Potential participants may take as long as they like to read through the consent form. Estimated time is 5min. Informed consent form will be accessed on REDCap Cloud. The study team's contact information is within the consent form if any questions come up. Fully signed consent forms can be obtained via download on the REDCap Cloud platform. REDCap Cloud can store signed consent forms and data securely. A copy of the signed consents may also be stored on Stanford Medicine Box. Study staff can send fully signed consent forms via secure email upon request. (iv) Yes. (v) Study staff will not be with the potential participant and there will be no possibility of coercion or undue influence. (vi) If under 18 years of age, the respondent is screened out before the consent form appears. Additionally, birth date is asked in the baseline survey.

b) What is the Procedure to assess understanding of the information contained in the consent? How will the information be provided to participants if they do not understand English or if they have a hearing impairment? See HRPP Chapter12.2 for guidance.

Only English fluent participants will be recruited. The Consent form will be readable and those with a hearing impairment will still be able to access the consent form.

c) What steps are you taking to determine that potential participants are competent to participate in the decision-making process? If your study may enroll adults who are unable to consent, describe (i) how you will assess the capacity to consent, (ii) what provisions will be taken if the participant regains the capacity to consent,(iii) who will be used as a legally authorized representative, and (iv) what provisions will be made for the assent of the participant.

The consent form will only be accessible to those who can meet screening criteria. Participation will only include those competent to consent in the low risk study.

Address the following regulatory criteria for a waiver of consent and provide protocol-specific justification for each:

1) Y The research/clinical investigation involves no more than minimal risk (as defined in 45 CFR 46.102(j), 21 CFR 50.3(k), or 21 CFR 56.102(i)) to the participants. [45 CFR 46.116(f)(3)(i) and/or 2017 FDA Guidance IV.1]

The study is a RCT with group blinding to test whether WSUDs is more effective in reducing problematic substance use than an education only control. The study will involve four questionnaires

Title : Woebot for Substance Use Disorders Phase 2 RCT: Digitally Delivered Intervention for Reducing Problematic Substance Use (SU sIRB) Short name: Anchor Study

Approval Period: 03/17/2023 - 05/11/2023

about physical and mental health, and substance use. Participation information will be coded and stored on compliant platforms (Stanford Medicine Box) and on encrypted, password protected computers. App data is protected with Woebot's security measures.

2) **The waiver or alteration will not adversely affect the rights and welfare of the participants. [45 CFR 46.116(f)(3)(iv) and/or 2017 FDA Guidance IV.2]**

Confidentiality and HIPAA practices will still be in place. Data is stored on compliant platforms (e.g. Qualtrics, Stanford Medicine Box) and on encrypted password protected computers.

3a) **The research/clinical investigation could not practicably be carried out without the requested waiver or alteration. [45 CFR 46.116(f)(3)(ii) and/or 2017 FDA Guidance IV.3]**

3b) **For research using identifiable private information or identifiable biospecimens, the research could not practicably be carried out without using such information or biospecimens in an identifiable format. [45 CFR 46.116(f)(3)(iii)]**

There will be intervention group blinding to maximize validity and minimize bias. To keep the group blinding effective, the groups are not fully described in the consent form, and full details of the group intervention a participant is randomized to will be provided after randomization. A debrief will be provided to participants after the 12-week assessment period.

4) **Whenever appropriate, the participants or legally authorized representatives will be provided with additional pertinent information after participation. [45 CFR 46.116(f)(3)(v) and/or 2017 FDA Guidance IV.4]**

Participants will be provided with a debrief of group blinding at the end of their study participation. This will be provided by email either be after completion of the final survey or a month after the final survey was due (for those who don't complete the final survey).

14. Assent Background (less than 18 years of age)

15. HIPAA Background

15.1 Alteration of Authorization

screening consent-alteration of authorization

a) **Describe the Protected Health Information (PHI) needed to conduct the research. PHI is health information linked to HIPAA identifiers. List BOTH health information AND HIPAA identifiers. If you are using STRIDE, use the Data Privacy Attestation to ensure that your request will match your IRB-approved protocol.**

For the screening: Alcohol and drug use, and related events Demographics (e.g. age, sex, race/ethnicity)
Past year suicide attempt or psychosis Name (consent process) Signature (consent process) Email (if eligible) Phone (if eligible)

b) Please Answer:

Do you certify that the use or disclosure of protected health information involves no more than a minimal risk to the privacy of individuals?

Do you certify that the research could not practically be conducted without the waiver?

Do you certify that you have adequate written assurances that the protected health information will not be reused or disclosed to any other person or entity, except as required by law, for authorized oversight of the research project, or for other research for which the use or disclosure of protected health information would be permitted?

Do you certify that the research could not practically be conducted without access to and use of the

protected health information?

c) Please describe an adequate plan to protect any identifiers from improper use and disclosure.

In the screening questionnaire, the study team will ask questions on alcohol and drug use (broadly), questions on demographics, and questions to ensure respondents are not high risk (e.g. past 12-month suicide attempt, psychosis). More sensitive questions will be grouped with less sensitive questions (e.g. high risk type questions will be in the same question group as pregnancy status).

d) Please describe an adequate plan to destroy the identifiers at the earliest opportunity consistent with conduct of the research, unless there is a health or research justification for retaining the identifiers or such retention is otherwise required by law.

Identifiers will be destroyed on December 31, 2045 or when the research project ends, whichever is earlier. This can be accomplished by deleting identifiers from the data set. If the data is coded, the codebook for identifiers is destroyed.

Woebot for Substance Use Disorders Phase 2 RCT: Digitally Delivered Intervention for
Reducing Problematic Substance Use

NCT ID: 04925570

March 17, 2023

Descriptive statistics (means, frequencies) will be run to describe the sample, and the balance achieved by the randomization, and to examine ratings of program feasibility and acceptability. Missing data on individual survey items is anticipated to be minimal. As needed, individual participants' average score values may be imputed when missing individual items on a scale (e.g., PHQ-8). For the outcomes of interest, the target estimand is the intent to treat on the study population with no loss to drop-out of the study (i.e., this estimand incorporates noncompliance with the randomization's assigned level of intervention). We will examine predictors of study retention. Generalized Linear Models (multivariable models) will test for group differences in changes in the primary outcome and secondary outcomes. The dependent variables will be baseline to EOT (and baseline to 1-month follow-up) change scores. The models are used to adjust for baseline group differences and will apply weights to adjust for correlates of study retention. Participant weights will be calculated as the inverse of predicted probability values from a logistic regression model predicting EOT (and 1-month follow-up) retention.

Between-subject differences in baseline variables may be substantial (e.g., baseline number of substance use occasions) so the models will use change from baseline to a given time point (e.g., number of substance use occasions at EOT minus the number of substance use occasions at baseline). This trial, while not an exact replication, extends previous work with a waitlist control where the primary outcome was the change in baseline to EOT in substance use occasions. Thus, we separately analyze changes (a) from baseline to EOT, and (b) from baseline to 1-month.

Correlations also will be examined between W-SUDs engagement metrics and change in primary and secondary outcomes in the treatment group. Additionally, a per-protocol analysis will be limited to treatment participants who use W-SUDs at least 4 of 8 weeks and control participants who view at least half of the online psychoeducational fact sheets.

Bivariate correlations will examine associations between changes in substance use problems and changes in use occasions, confidence, depression, anxiety, and work productivity scores. Participants will be prompted to report craving within W-SUDs daily. If participants provide multiple craving ratings within a day, the scores will be averaged for that day. To examine changes over time in daily craving ratings, generalized estimating equation (GEE) linear models will be run with week entered as a factor, setting week 1 as the reference category.

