Phase I (N=101) has concluded and a manuscript is in submission. In this study, W-SUDs was feasible to deliver, engaging, and acceptable; and associated with significant improvements in substance use, confidence, cravings, depression, and anxiety. Study attrition was high.

The supplemental study (W-C19) is a randomized control trial with a wait-list control condition. This study aimed to expand understanding of W-SUDs' performance among users experiencing SUDs whilst contributing to our overall understanding of COVID-19's impact upon this population. The intervention had concluded with N=180 participants enrolled. Experiencing worsened mental health symptoms during COVID-19 was associated with more substance use problems and depression and anxiety symptoms. Pandemic disruptions may exacerbate preexisting substance use problems.

Phase II will evaluate the efficacy of W-SUDs in a large scale RCT relative to an education-only control condition. Primary outcomes will be measures of the quantity and frequency of substance use including, number of substance use occasions, heavy drinking days (if applicable), percent days abstinent. Additionally, phase II will evaluate whether W-SUDs results in a greater reduction in substance-related problems than Education Only control and explore: Does engagement with W-SUDs, relative to education-only control (a) improve symptoms of depression and anxiety (b) improve work productivity (i.e. reduce presenteeism/absenteeism), (c) reduce cravings, (d) improve situational confidence. Phase II will also allow the team to learn more about the population interested in digitally delivered interventions.

Impact

Immediate access to a digital therapeutic in a resource constrained, social distance healthcare ecosystem amidst growing psychological challenges in this already vulnerable and underserved population.

Elements of our W-C19 program have already been integrated into W-SUDs because we felt that it was timely and appropriate to address users' concerns about the pandemic and demonstrated that Woebot was 'intelligent' to the current crisis.

c) **Explain why human subjects must be used for this project. (i.e. purpose of study is to test efficacy of investigational device in individuals with specific condition; purpose of study is to examine specific behavioral traits in humans in classroom or other environment)**

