3. Risk of treatment avoidance due to engagement with either of the randomized interventions. In both interventions it is explicitly stated that the service should not be used in place of traditional treatment. [REDACTED]

4. Risk of suicide: Woebot informs the participant that it is not designed for crisis service. [REDACTED]

Additionally, if anyone is developing or indicating serious thoughts about suicide or harming themselves, it is best practice to call 9-1-1 and/or go to the nearest ER.

d) Explain the point at which the experiment will terminate. If appropriate, include the standards for the termination of the participation of the individual participant Also discuss plans for ensuring necessary medical or professional intervention in the event of adverse effects to the participants.

IRB Modification 12/19/2022: The study will terminate once the 3-month period with all 400 eligible participants has been completed and the analyses run and submitted for publication.

Participants can refuse to participate at any time.

When we learn of a participant's adverse event, the team will report the adverse event and may follow up with the participant for additional information. Resources will be offered. The EOT and 12-week surveys includes questions that assess for SAEs. More details about adverse events are in section e.

e) Data Safety and Monitoring Plan (DSMP). See guidance on Data Safety and Monitoring.

A Data and Safety Monitoring Plan (DSMP) is required for studies that present Medium or High risk to participants. (See Overall Evaluation of Risk above). If Low Risk, a DSMP may not be necessary. Multi-site Phase III clinical trials funded by NIH require the DSM Plan to have a Data Safety

Title : Woebot for Substance Use Disorders Phase 2 RCT: Digitally Delivered Intervention for Reducing Problematic Substance Use (SU sIRB) Short name: Anchor Study

Approval Period: 03/17/2023 - 05/11/2023

Monitoring Board or Committee (DSMC or DSMB). The FDA recommends that all multi-site clinical trials that involve interventions that have potential for greater than minimal risk to study participants also have a DSMB or DSMC.

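### The SAP handles baseline variation by change scores and does not name the outcome's own baseline as a covariate; leaving it out would give up precision that is free to recover.

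*SAP*

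**What the plan says.** All the relevant text is in the SAP's account of the outcome analysis.

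- **Models in scope:** "Generalized Linear Models (multivariable models) will test for group differences in changes in the primary outcome and secondary outcomes".
- **Dependent variable:** "The dependent variables will be baseline to EOT (and baseline to 1-month follow-up) change scores". The two time points are analysed separately.
- **Reason for change scores:** "Between-subject differences in baseline variables may be substantial (e.g., baseline number of substance use occasions) so the models will use change from baseline". A second reason is continuity, since the trial "extends previous work with a waitlist control where the primary outcome was the change in baseline to EOT in substance use occasions".
- **Covariates and weights:** "The models are used to adjust for baseline group differences and will apply weights to adjust for correlates of study retention". No covariate is listed, and the outcome's own baseline is neither included nor excluded.

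Protocol section 1(b) lists the primary measures as "number of substance use occasions, heavy drinking days (if applicable), percent days abstinent". Protocol section 2(a) places the baseline survey before randomisation, so the baseline value is known for everyone randomised.

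**The concern.** Subtracting baseline is not the same as adjusting for it. A change score assumes that a participant one unit higher at baseline will, on average, be one unit higher at follow-up. If the true slope is lower, as when high values regress towards the mean, subtraction over-corrects and leaves baseline noise in the arm comparison. A model containing the baseline value estimates the slope instead.

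The covariate sentence does not settle which analysis is planned. It ties adjustment to differences between the groups, so an analyst could add baseline only for outcomes that look imbalanced, or omit it because subtraction has already used it. Baseline adjustment gains precision when the arms are balanced too, so observed imbalance is the wrong trigger.

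At stake is the width of the intervals for the between-arm primary and secondary comparisons at both time points. The daily craving analysis within the W-SUDs arm ("generalized estimating equation (GEE) linear models will be run with week entered as a factor") and the planned correlations are not affected.

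**Working it through.** **Inputs.** The planned number is 400 (Protocol sections 8(a) and 9(d): "The study will terminate once the 3-month period with all 400 eligible participants has been completed"). The documents give no SD, no baseline-to-follow-up correlation and no power calculation, so there is no stated figure to reproduce. I assume a correlation ρ from 0.3 to 0.9 and a ratio s of follow-up SD to baseline SD of 0.8, 1.0 or 1.2.

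**Formulas.** Set the baseline SD to 1. The slope of follow-up on baseline is then ρs. Per-participant variances are:

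- change score alone: V₁ = 1 + s² − 2ρs
- own baseline included: V₂ = s²(1 − ρ²)
- difference: V₁ − V₂ = (1 − ρs)², which is zero only when the slope is 1
- loss = (1 − ρs)² / V₁
- interval widening = 1/√(1 − loss) − 1
- equivalent n = 400 × (1 − loss), with no dropout and no weights

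**Worked case, ρ = 0.5, s = 1.** V₁ = 1 + 1 − 1 = 1.00. V₂ = 1 × (1 − 0.25) = 0.75. Loss = 0.25/1.00 = 25%. Widening = 1/√0.75 − 1 = 15.5%. Equivalent n = 400 × 0.75 = 300.

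| s | ρ | slope | loss | wider interval | equivalent n |
|---|---|---|---|---|---|
| 0.8 | 0.3 | 0.24 | 49.8% | 41.1% | 201 |
| 0.8 | 0.5 | 0.40 | 42.9% | 32.3% | 229 |
| 0.8 | 0.7 | 0.56 | 37.2% | 26.2% | 251 |
| 0.8 | 0.8 | 0.64 | 36.0% | 25.0% | 256 |
| 0.8 | 0.9 | 0.72 | 39.2% | 28.2% | 243 |
| 1.0 | 0.3 | 0.30 | 35.0% | 24.0% | 260 |
| 1.0 | 0.5 | 0.50 | 25.0% | 15.5% | 300 |
| 1.0 | 0.7 | 0.70 | 15.0% | 8.5% | 340 |
| 1.0 | 0.8 | 0.80 | 10.0% | 5.4% | 360 |
| 1.0 | 0.9 | 0.90 | 5.0% | 2.6% | 380 |
| 1.2 | 0.3 | 0.36 | 23.8% | 14.6% | 305 |
| 1.2 | 0.5 | 0.60 | 12.9% | 7.2% | 348 |
| 1.2 | 0.7 | 0.84 | 3.4% | 1.7% | 386 |
| 1.2 | 0.8 | 0.96 | 0.3% | 0.2% | 399 |
| 1.2 | 0.9 | 1.08 | 2.3% | 1.2% | 391 |

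The loss is exactly zero at slope 1, for example s = 1.2 and ρ = 1/1.2 = 0.83.

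**In terms of power.** Assume equal SDs, 1:1 allocation and a two-sided 5% test. Where the baseline-adjusted analysis has 80% power, the change score alone has 62%, 68% and 73% at ρ = 0.3, 0.5 and 0.7.

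**Simulation without dropout** (4,000 trials, 200 per arm, ρ = 0.5, s = 1). The variance ratio of adjusted to unadjusted was 0.748, against 0.75 from the formula.

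**Simulation with retention weights.** Assumptions: 400 randomised 1:1, about 69% retained, log-odds of retention falling 0.4 per baseline SD, inverse-probability weights, no true effect, 8,000 trials per cell. Losses at ρ = 0.3, 0.5 and 0.7 were 35/25/15% (s = 1.0), 51/44/38% (s = 0.8) and 24/13/4% (s = 1.2). Both estimators averaged about zero (largest absolute mean 0.0025). The weights therefore do not replace baseline adjustment.

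**Change or follow-up as outcome.** With the own baseline in the model, the arm coefficient was the same for either, to within 1e-15.

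**The case against.** The strongest reply is that the SAP is ambiguous rather than wrong. The models are multivariable and adjust for baseline differences, which may already include the outcome's own baseline. That is a fair reading, and under it only clarification is needed. But the text does not compel it, and two analysts could follow this SAP and report different primary intervals.

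Second, the loss figures describe a change score with no covariates. Other baseline covariates could recover part of the loss. Take ρ = 0.5, equal SDs, and one covariate related to follow-up only through the own baseline, with correlation r to it. The loss is then 0.25(1 − r²)/[0.25(1 − r²) + 0.75], which is 20% at r = 0.5 and 14.5% at r = 0.7, against 25% with no covariate. This stands: the table applies to change alone. The own baseline would still add precision in that example.

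Third, the size is unknown. The computed range runs from 0.3% to 50%, zero is possible, and the participant counts assume no dropout although the Protocol (section 1(b)) calls Phase I attrition high. This stands too. The percentages barely moved under the dropout simulated; the counts would shrink with the analysed sample.

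Fourth, the statement that the loss is never negative needs a common slope across arms or equal allocation, and the documents give no allocation ratio. This is an edge case. Likewise, the absence of bias after dropout rests on the retention model, with or without the own baseline.

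Finally, the SAP speaks of a single primary outcome where the Protocol lists three measures. The argument does not depend on which is meant, because it applies to each outcome separately.

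**Conclusion.** The point holds as a matter of precision. The SAP makes subtraction its method for large baseline variation, and nothing in either document puts the outcome's own baseline into the models. If it is left out, intervals are wider than the same data allow wherever the slope differs from 1. The documents give no reason to expect a slope of 1 for every outcome at both time points.

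With equal SDs and ρ from 0.3 to 0.7, the loss for change alone is 35% to 15%, and intervals are 24% to 8.5% wider. If spread falls at follow-up the loss is larger; if spread rises it is smaller in this range of ρ. These are large-sample figures for a linear model with assumed ρ and s, so the actual loss in this trial is undetermined. Under randomisation the planned contrast is unbiased before dropout. The change should be made, but the validity of the trial does not depend on it.

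**What to change.** Add two sentences to the SAP, along these lines:

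> Each between-arm model of a primary or secondary change score (identity link) will include the baseline value of that same outcome as a covariate, at EOT and at 1 month, whether or not the arms differ on it. Any other covariates are listed here and fixed before the arms are compared.

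The SAP does not state a link; identity is natural for change scores, which can be negative, and the equality of the arm coefficients for change and follow-up relies on it. The second sentence closes the gap left by the missing covariate list.

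The cost is one degree of freedom per model. No new data are needed, because the baseline value is already required to form the change score. Change from baseline can still be reported, so continuity with the waitlist trial is kept, and the retention weights stay as planned.
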